##### 3.1.1. Study Design

Prospective, Randomized (1:1), Controlled, Multi-center study for AVF Peripheral cohort in which subjects will be randomized to receive treatment with the WRAPSODY Endovascular Stent Graft System or PTA. In addition, a separate arm of the trial will include a prospective, single arm, multi-center study for the AVG anastomosis cohort in which subjects will receive treatment with the WRAPSODY Endovascular Stent Graft System.

##### 3.1.2. Enrollment

Up to a total of 357 subjects across both cohorts allowing for a sufficient number of evaluable subjects at six (6) months. At least 60% of the subjects must come from the US for each cohort (40% OUS). No site may enroll more than 20% of the total population for a specific cohort. There are two cohorts for the trial:

1. Up to 244 AVF Peripheral Subjects (1:1 randomization, with approximately 122 in the study treatment and control groups)
2. Up to 113 AVG Anastomosis Subjects (no randomization, comparison to Performance Goal)

##### 3.1.3. Study Population

The study comprises two (2) independent cohorts: 1) Subjects with AVF for hemodialysis who have stenosis or occlusion of the peripheral venous outflow circuit, including the cephalic arch; and 2) subjects with AVG for hemodialysis who have stenosis or occlusion at the graft-vein anastomosis or juxta-anastomosis. Juxta-anastomosis is defined as a location such that the PTA balloon or WRAPSODY Stent Graft cross the anastomosis.

#### 3.2 Study Duration and Follow-Up

The study commenced enrollment in March 2021. Enrollment is expected to continue until December 2023, at which time it is anticipated that all cohorts would be completely enrolled. Study subjects will be required to return for clinic visits post-procedure at Day 30 ( $\pm 10$  days), Month 6 (180 days  $\pm 30$  days), Month 12 (360 days  $\pm 45$  days) and Month 24 (720 days  $\pm 75$  days). Several telephone visits will be completed as well at Months 3 (90 days  $\pm 15$  days), 9 (270 days  $\pm 30$  days) and 18 (540 days  $\pm 45$  days). The 24-month visit is expected to be in the post-market surveillance phase of the study. In addition, this study shall meet the Post-Market Study requirements for CE Marking. All subjects will be followed according to the Schedule of Events in Table 9. The last follow-up visit is expected to be completed by January 2026, at the last subject's 24-month follow-up visit.

## 4.0 STUDY ENDPOINTS AND SUBJECT POPULATION

### 4.1 Primary Outcome Measures

[figure not shown]
#### 4.1.1. Primary Safety Endpoint

The primary outcome measure for safety in the WAVE Study is proportion of subjects without any localized or systemic safety events through 30 days post-procedure that affect the access or venous outflow circuit and resulted in reintervention, hospitalization, or death (not including stenosis or thrombosis). Endovascular procedures performed to treat safety events after the index study procedure will be considered surgeries.

#### 4.1.2. Primary Effectiveness Endpoint

The primary outcome measure for effectiveness in the WAVE Study is Target Lesion Primary Patency (TLPP) at 6 months. Target Lesion Primary Patency defined as freedom from clinically-driven target lesion revascularization (CD-TLR) or target lesion thrombosis measured through 6 months post-procedure, which is the time interval of uninterrupted patency after study procedure to the next intervention performed on the target lesion or uncorrectable target lesion occlusion.

### 4.2 Secondary Outcome Measures

1. Proportion of subjects with Target Lesion Primary Patency at months 12 and 24.
  2. Proportion of subjects with Assisted Target Lesion Primary Patency (aTLPP) at months 6, 12 and 24 defined as time to loss of Assisted Primary Patency of the target lesion, which is the time from post-procedure until uncorrectable target lesion occlusion.
  3. Proportion of subjects with Access Circuit Primary Patency (ACPP) at months 6, 12 and 24 defined as time to loss of Primary Patency of the access circuit, which is the time from post-procedure until any venous outflow circuit re-intervention, or access thrombosis or abandonment.
  4. Proportion of subjects with Post-Procedure Secondary Patency at months 6, 12 and 24 defined as the interval post-procedure until access circuit abandonment.
  5. Rates of procedure- and device-related adverse events involving the access circuit at index procedure, 30 days, and months 6, 12 and 24.
- 

[figure not shown]
[figure not shown]

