Secondary Outcome Measures:	
 
Proportion of subjects with Target Lesion Primary Patency at months 12 and 24.
 
Proportion of subjects with Assisted Target Lesion Primary Patency (aTLPP) at months 6, 12 and 24 defined as time to loss of Assisted Primary Patency of the target lesion, which is the time from post-procedure until uncorrectable target lesion occlusion.
 
Proportion of subjects with Access Circuit Primary Patency (ACPP) at months 6, 12 and 24 defined as time to loss of Primary Patency of the access circuit, which is the time post-procedure until any venous outflow circuit re-intervention, or access thrombosis or abandonment.
 
								

	
4. Proportion of subjects with Post-Procedure Secondary Patency at months 6, 12 and 24 defined as the interval post-procedure until access circuit abandonment.
 
5. Rates of procedure- and device-related adverse events involving the access circuit at index procedure, 30 days, and months 6, 12 and 24.
 
[REDACTED]

Exploratory Endpoints:	
[REDACTED]

Inclusion Criteria:	
 
1. Subject provides written informed consent before any study-specific investigations or procedures.
 
2. Subject is male or female, with an age <math>\geq 18</math> years at date of enrollment.
 
3. Subject is willing to undergo all follow-up assessments according to the specified schedule over 24 months.
 
4. Subject has a life expectancy <math>\geq 12</math> months.
 
5. Subject is undergoing chronic hemodialysis.
 
6. Subject has either a mature AVF or AVG in the arm that has been created <math>\geq 30</math> days prior to the index procedure and has completed at least one successful dialysis session.
 
7. Subject has clinical and/or hemodynamic evidence of a venous outflow obstruction or AV fistula or graft dysfunction.
 

Angiographic Inclusion Criteria:	
[REDACTED]

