**Arteriovenous (AV) Access Abandonment:** When a vascular access can no longer be used for prescribed 1 or 2 needle dialysis because it is unable to provide adequate flows and/or is deemed unsafe for the patient, and the associated problem cannot be corrected by any intervention, including medical, surgical, or radiologic interventions or rest (KDOQI).

**Assisted Target Lesion Primary Patency (aTLPP):** Defined as time to loss of Assisted Primary Patency of the target lesion, which is the time from post-procedure until uncorrectable target lesion occlusion.

**Bleeding Complication (Major):** Bleeding resulting in  $\geq 3$  g/dl decrease in hemoglobin (if hemoglobin level not available, a decrease in hematocrit of  $\geq 10\%$ ), or necessitating transfusion of  $>1$  unit of PRBC's / whole blood or necessitates surgery/endoscopic intervention.

**Access site:** Bleeding from the arteriotomy site which requires transfusion, hospitalization (either admission or extended stay), or further treatment for management.

**Cardiac Arrhythmia:** Electrical disruption of the heart rhythm requiring specific medication, DC shock, or pacemaker insertion to address condition.

**Cardiogenic Shock:** Subject presents with SBP  $< 80$  mm Hg for more than 30 minutes unresponsive to fluids or requiring intravenous vasopressor agent or an intra-aortic balloon pump (IABP).

**Catheter Dysfunction:** The first occurrence of either (1) peak blood flow of 200 ml per minute or less for 30 minutes during a dialysis treatment, (2) mean blood flow of 250 ml per minute or less during two consecutive dialysis treatments, or (3) inability to initiate dialysis owing to inadequate blood flow, after attempts to restore patency have been attempted.

**Cerebral Vascular Accident (CVA):** See Stroke.

**Closure, Abrupt:** Occurrence of new (during the index procedure), persistent slow, reduced, or loss of flow within the target vessel that requires intervention other than the index or adjunct treatment. Abrupt closure may also be referred to as acute occlusion if there is a total loss of flow.

**Closure, Late:** Target lesion site occlusion that occurs greater than 30 days after the index procedure is completed (e.g., the subject has left the treatment area).

**Closure, Subacute:** Target lesion site occlusion that occurs after the index procedure is completed (e.g., the subject has left the treatment area) and within 30 days of procedure.

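### Assisted target lesion primary patency is lost only at uncorrectable occlusion, so a target lesion that thromboses and is reopened still counts as assisted-primary patent

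*Combined protocol and SAP*

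**What the plan says.** Section 4.2 lists aTLPP as a secondary outcome at months 6, 12 and 24. Its time to loss is the one "which is the time from post-procedure until uncorrectable target lesion occlusion". The Protocol Summary and section 13.0 carry the same definition, and none of the three names thrombosis. The word uncorrectable is not defined.

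The neighbouring measures are worded differently:

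- TLPP, in section 4.1.2, is "freedom from clinically-driven target lesion revascularization (CD-TLR) or target lesion thrombosis measured through 6 months post-procedure".
- ACPP, in section 4.2, runs "until any venous outflow circuit re-intervention, or access thrombosis or abandonment".
- Post-Procedure Secondary Patency, in section 4.2, is "defined as the interval post-procedure until access circuit abandonment". Section 13.0 defines abandonment as an access that is unusable or unsafe where "the associated problem cannot be corrected by any intervention, including medical, surgical, or radiologic interventions or rest".

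Section 9.10 leaves aTLPP out of the hierarchical testing list, so it is summarized descriptively.

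**The concern.** The plan calls aTLPP a form of primary patency, and both of its other primary patency measures fail at thrombosis. Forgiving a reintervention on a lesion that is still open is what the word assisted suggests. The definition goes further and forgives every thrombosis or occlusion that can be reversed.

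Section 1.4 names stenosis followed by thrombosis among the main complications of fistulas and says that thrombosis is more frequent in grafts. In the randomized AVF cohort, the two arms could differ widely in corrected target lesion thromboses and still show identical aTLPP. At stake is the meaning of a named secondary endpoint at three time points: a high figure could be taken as freedom from lesion thrombosis, which it does not measure.

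**Working it through.** The plan states no figure for aTLPP, so there is none to reproduce. The check has two parts.

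**1. Definitions side by side**

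| Measure | Level | Lost at | Lost when a target lesion thromboses and is reopened? |
|---|---|---|---|
| TLPP (4.1.2) | lesion | clinically driven revascularization, or target lesion thrombosis | yes |
| ACPP (4.2) | circuit | outflow reintervention, access thrombosis, or abandonment | yes |
| aTLPP (Protocol Summary, 4.2, 13.0) | lesion | uncorrectable target lesion occlusion | no |
| Secondary patency (4.2) | circuit | abandonment | no |

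On reopened thrombosis, aTLPP falls with secondary patency and not with the primary measures. This follows from the text alone.

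**2. Where aTLPP sits relative to secondary patency**

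Section 9.8 gives the rate: events divided by subjects with sufficient follow-up plus subjects with an event. Section 5.4 has subjects withdrawn at abandonment. For one AVF arm of N = 122 (section 9.7), let

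- U = uncorrectable target lesion occlusion leading to abandonment,
- A = abandonment for another cause, withdrawn before the milestone without an aTLPP event,
- B = uncorrectable target lesion occlusion with the access still in use,
- T = target lesion thrombosed and reopened, with no other aTLPP failure.

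Everyone else is taken as fully followed. Then

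- aTLPP as defined = 1 − (U + B)/(N − A)
- aTLPP if thrombosis ended it = 1 − (U + B + T)/(N − A)
- secondary patency = 1 − (U + A)/N

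*Case B = 0.* aTLPP is at or above secondary patency when U/(N − A) ≤ (U + A)/N. This reduces to 0 ≤ A(N − U − A), which always holds because U + A cannot exceed N. A grid of all 1,681 combinations of U and A from 0 to 40 showed no exception. The two are equal when A = 0.

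*Case B > 0.* The order reverses when B × N > A(N − U − A). With U = 2 and A = 4 the right side is 4 × 116 = 464, and 464/122 = 3.8, so B of 4 or more reverses it.

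The documents give no rates for these events, so all counts below are assumptions:

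| U | A | B | T | aTLPP as defined | aTLPP if thrombosis ends it | Secondary |
|---|---|---|---|---|---|---|
| 2 | 4 | 0 | 6 | 1 − 2/118 = 98.3% | 1 − 8/118 = 93.2% | 1 − 6/122 = 95.1% |
| 2 | 4 | 0 | 12 | 98.3% | 1 − 14/118 = 88.1% | 95.1% |
| 2 | 4 | 3 | 12 | 1 − 5/118 = 95.8% | 85.6% | 95.1% |
| 2 | 4 | 6 | 12 | 1 − 8/118 = 93.2% | 83.1% | 95.1% |
| 2 | 0 | 1 | 12 | 1 − 3/122 = 97.5% | 87.7% | 1 − 2/122 = 98.4% |

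The first two rows show that aTLPP as defined does not move with T. The gap between the two versions is T/(N − A): 6/118 = 5.1 points and 12/118 = 10.2 points.

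**The case against.** The strongest defence is that the definition is deliberate and coherent. It is the same in all three places. The TLPP sentence in section 4.1.2 ends at the next target lesion intervention or at uncorrectable occlusion; aTLPP keeps the second limb and forgives interventions. Nothing in the documents says that an assisted measure must lie between primary and secondary patency. A lesion-level figure above a circuit-level one is not in itself an error. All of this stands, and there is no internal contradiction in the aTLPP wording. It does not answer the narrower point: the measure carries the name primary patency but ignores an event that ends both of the plan's other primary patency measures.

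A reader might infer three stronger things that the documents do not support.

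- *That aTLPP must sit at or above secondary patency.* This requires every uncorrectable target lesion occlusion to lead to abandonment. If some accesses stay in use around an occluded lesion, the order can reverse, as the last two rows of the table show.
- *That no secondary endpoint captures thrombosis-free maintenance.* Text after the fifth secondary outcome is blacked out or missing, and the exploratory endpoints are blacked out. The visible TLPP, ACPP and access-circuit adverse event outcomes also capture thrombosis, though within composites or safety rates.
- *That aTLPP is overstated by a known amount, or sits near its ceiling.* The documents give no rate for thrombosis, uncorrectable occlusion or abandonment.

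**Conclusion.** The point holds in limited form. As defined, aTLPP does not fail when a target lesion thromboses and is reopened, and no visible section changes that; the CEC Charter is not among the documents. The endpoint therefore cannot distinguish a lesion kept open from one that clotted and was rescued. It acts as a lesion-level secondary patency, and its expected position at or above Post-Procedure Secondary Patency rests on uncorrectable lesion occlusion usually ending the access.

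Its size is the share of subjects whose only aTLPP failure would be a corrected target lesion thrombosis, one percentage point for each 1% of evaluable subjects. The 5.1 and 10.2 points above illustrate this with assumed counts; they are not estimates.

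Because aTLPP is descriptive, cohort success, the primary endpoint, the type I error plan and the sample size are untouched. The matter should be corrected, but it does not threaten the trial's main conclusions.

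**What to change.** In the Protocol Summary, section 4.2 and section 13.0, define aTLPP as the time from the index procedure to the first target lesion thrombosis or occlusion, whether or not it is later corrected. State that reinterventions on a target lesion that is still open are not failures. Leave Post-Procedure Secondary Patency ending at abandonment.

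Three details belong with the change:

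- Use target lesion thrombosis, as in section 4.1.2, and reconcile the TLPP entry in section 13.0, which refers to access circuit thrombosis. Section 13.0 defines thrombosis only at circuit level, so add a rule for attributing it to the target lesion.
- Enrollment began in March 2021 (section 3.2), and neither physicians nor subjects are blinded (section 6.4.3). Also report time to uncorrectable target lesion occlusion, the present definition, under a separate name.
- Define uncorrectable for that retained measure.

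The data burden should be small. Target lesion thrombosis is already a primary endpoint component, section 12.10 has the CEC review all pre-specified endpoints and conduit interventions through end of study, and section 7.3.2 follows access circuit events to 24 months. The costs are a protocol amendment, which may need FDA and IRB/EC approval under section 12.3, the attribution rule, and an aTLPP figure that will be lower if any such thromboses occur.

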#### 4.4 Eligibility Criteria

Subjects in both cohorts are required to meet ALL of the following inclusion criteria and NONE of the exclusion criteria in order to be included in this clinical trial:

##### 4.4.1. General Inclusion Criteria

1. Subject provides written informed consent before any study-specific investigations or procedures.
2. Subject is male or female, with an age  $\geq 18$  years at date of enrollment.
3. Subject is willing to undergo all follow-up assessments according to the specified schedule over 24 months.
4. Subject has a life expectancy  $\geq 12$  months.
5. Subject is undergoing chronic hemodialysis.
6. Subject has either a mature AVF or AVG in the arm that has been created  $\geq 30$  days prior to the index procedure and has completed at least one successful dialysis session.
7. Subject has clinical and/or hemodynamic evidence of a venous outflow obstruction or AV fistula or graft dysfunction.

##### 4.4.2. Angiographic Inclusion Criteria

- 
6. Target lesion reference vessel diameter is between 5.0 mm and 14.0 mm by operator's visual estimate.
- 

##### 4.4.3. General Exclusion Criteria

[figure not shown]
3. Subject has a known or suspected infection of the hemodialysis access site, systemic infection and/or septicemia.

7. Subject has a history of unstable angina or myocardial infarction within 60 days prior to enrollment.

[figure not shown]

10. Subject is pregnant, breastfeeding, or intending to become pregnant within the next year.

#### **4.4.4. Angiographic Exclusion Criteria**

1. Target lesion is located within a stent / stent graft.

## 5.0 STUDY SCREENING AND ENROLLMENT

### 5.1 Subject Screening

All patients presenting to the institution with known arteriovenous access circuit stenosis requiring an interventional procedure shall be evaluated for eligibility and participation in the study. A member of the research team shall perform a preliminary evaluation of the potential subject's medical history and previously performed examinations to assess for initial eligibility. If the patient is willing to participate in the study, a written consent will be obtained. No study-specific requirements will be performed prior to obtaining informed consent.

### 5.2 Informed Consent

Written Informed Consent with the Institutional Review Board (IRB) or Ethics Committee (EC) approved consent form will be obtained for all subjects **prior** to any study-specific screening/baseline tests or procedures being performed. This does not include those procedures or tests that are obtained in the normal course of the subject's non-study related care and prior to undergoing the study procedure. The subject shall be given adequate time to read the informed consent form, have the study procedures explained, including the risks, benefits and follow-up requirements prior to signing the Informed Consent documents. All subjects providing informed consent are to receive a copy of their signed informed consent. The consent process may be obtained up to 30 days prior to index / treatment procedure.

[figure not shown]
### 5.3 Subject Enrollment

All patients requiring an intervention due to reasons detailed in this protocol are potential study candidates and shall be screened for eligibility. Every effort will be made to ensure eligibility prior to enrollment. According to ISO 14155:2020, enrollment in the study occurs at the time of informed consent; however, for the purposes of this study, only subjects who are consented and meet all the study inclusion criteria and none of the study exclusion criteria and are treated, or treatment is attempted with the study device or randomized, will be considered enrolled into the study. Therefore, the enrollment date (Day 0) will be the date of the study index procedure; the enrollment date will not be the date of informed consent for this study. Subjects who do not meet all inclusion and exclusion criteria (e.g., including: (i) operator is unable to successfully predilate the lesion; (ii) either target reference vessel diameter or target lesion length are outside the eligible parameters, etc.) will be considered an angiographic screen failure and will not be followed in the study (no data will be collected on these subjects). Subjects in whom the WRAPSODY Endovascular Stent Graft System is inserted into the vasculature and the treatment of the target lesion is attempted, but the procedure is aborted without delivery of a stent graft, will be followed through discharge for safety only and the subject will be allowed to exit the study. No additional study required assessments shall be collected. These subjects will be replaced.

Subjects randomized to PTA who experience perforation, rupture or significant dissection requiring intervention beyond PTA (i.e., requires treatment with bare metal stent, non-study stent graft, drug-eluting balloon) will followed through discharge for safety only and the subject will be allowed to exit the study. No additional study required assessments shall be collected as the subject would not be able to be assessed for study endpoints. These subjects will be replaced.

Subjects who are enrolled and treated, but who are later discovered to not meet all of the study criteria will remain in the study and complete all of the study testing and follow-up requirements. A Protocol Deviation will be completed for study subjects who are found to be ineligible after enrollment.

**Refer to Figure 6:** Enrollment Diagram:

